## 10.9. Appendix 9: Abbreviations and Definitions

Term	Definition
abuse	Use of a study intervention for recreational purposes or to maintain an addiction or dependence
AE	adverse event
ALP	alkaline phosphatase
ALT	alanine aminotransferase
AST	aspartate aminotransferase
AUC	area under the concentration versus time curve
AUC(0-tlast)	AUC from time 0 to the last measurable concentration after the first dose
AUC(0-∞)	AUC from time 0 to infinity
Cmax	maximum observed drug concentration
complaint	A complaint is any written, electronic, or oral communication that alleges deficiencies related to the identity, quality, purity, durability, reliability, safety or effectiveness, or performance of a drug or drug delivery system.
compliance	Adherence to all study-related, good clinical practice (GCP), and applicable regulatory requirements.
CP	clinical pharmacologist
CRF	case report form; a printed, optical, or electronic document designed to record all of the protocol-required information to be reported to the sponsor for each trial participant.
CRP	clinical research physician: Individual responsible for the medical conduct of the study. Responsibilities of the CRP may be performed by a physician, clinical research scientist, global safety physician, or other medical officer.
CRU	clinical research unit
CT	computed tomography
device deficiencies	equivalent to product complaint
ECG	electrocardiogram
eCRF	electronic case report form
enroll	The act of assigning a participant to a treatment. Participants who are enrolled in the study are those who have been assigned to a treatment.

enter	Participants entered into a study are those who sign the informed consent form directly or through their legally acceptable representatives.
GCP	good clinical practice
GI	gastrointestinal
GIP	gastric inhibitory polypeptide
GLP	glucagon-like peptide
IB	investigator's brochure
ICF	informed consent form
ICH	International Council for Harmonisation
IEC	independent ethics committee
INR	international normalization ratio
informed consent	A process by which a participant voluntarily confirms their willingness to participate in a particular study, after having been informed of all aspects of the study that are relevant to the participant's decision to participate. Informed consent is documented by means of a written, signed, and dated informed consent form.
investigational product	A pharmaceutical form of an active ingredient or placebo being tested or used as a reference in a clinical trial, including products already on the market when used or assembled (formulated or packaged) in a way different from the authorized form, or marketed products used for an unauthorized indication, or marketed products used to gain further information about the authorized form. See also "IMP."
IRB	institutional review board
ISR	injection-site reaction
medication error	Errors in the prescribing, dispensing, or administration of a study intervention, regardless of whether or not the medication is administered to the participant or the error leads to an AE. Medication error generally involve a failure to uphold 1 or more of the 5 "rights" of medication use: the right participant, the right drug, the right dose, right route, at the right time.
	In addition to the 5 core rights, the following may also represent medication errors:
	
 
• dose omission associated with an AE or a product complaint
 
• dispensing or use of expired medication
 
• use of medication past the recommended in-use date
 
• dispensing or use of an improperly stored medication
 
• use of an adulterated dosage form or administration technique inconsistent with the medication's labeling (eg, Summary of Product Characteristics, IB, local label, protocol), or
 
• shared use of cartridges, prefilled pens, or both.
 

misuse	Use of a study intervention for self-treatment that either is inconsistent with the prescribed dosing regimen, indication, or both, or is obtained without a prescription
MUPFP	multi-use prefilled pen
participant	Equivalent to CDISC term “subject”: an individual who participates in a clinical trial, either as recipient of an investigational medicinal product or as a control
PK/PD	pharmacokinetics/pharmacodynamics
QW	once weekly
RA	receptor agonist
SAE	serious adverse event
SAP	statistical analysis plan
SC	Subcutaneous
SoA	schedule of activities
screen	The act of determining if an individual meets minimum requirement to become part of a pool of potential candidates for participation in a clinical study.
SDP	single-dose pen
T2DM	type 2 diabetes mellitus
TBL	total bilirubin
tmax	time to C max
ULN	upper limit of normal
WOCBP	Women of childbearing potential

7. References	18

Version history

The statistical analysis plan for GPIP is based on the protocol dated 10/21/2022.

Table 1 SAP Version History Summary

SAP Version	Approval Date	Change	Rationale
1		Not Applicable	Original version

1. Introduction

This document is the SAP for Study I8F-MC-GPIP.

The purpose of this study is to evaluate the PK of tirzepatide bioequivalence between fixed-dose multi-use prefilled pen (MUPFP) (test) versus a single-dose pen (SDP) (reference).

This SAP supersedes all statistical considerations and analyses described in Protocol GPIP.

1.1. Objectives, Endpoints

Objectives	Endpoints
Primary	

• To evaluate the bioequivalence between the MUPFP (test) and the SDP (reference), as assessed using tirzepatide PK in healthy participants	
• C_{max}, $AUC_{(0-t)}$, $AUC_{(0-\infty)}$
Secondary	

• To evaluate the additional PK parameter• To evaluate the safety and tolerability of a single subcutaneous dose of tirzepatide administered through MUPFP (test) versus SDP (reference)	
• t_{max}• Incidence of AEs

1.2. Study Design

[figure not shown]
This is a multicenter, open-label, randomized, 2-period, 2-sequence, crossover study conducted in healthy participants.

The study will include 2 treatment arms. Approximately 65 participants may be enrolled so that at least 54 participants complete the study. Participants will be randomly assigned 1:1 to the 2 treatment sequences. It is intended that approximately the same number of participants will be randomly assigned into each treatment sequence. The treatment sequence is:

- a single dose of 5 mg tirzepatide administered SC via MUPFP followed by SDP; or
- a single dose of 5 mg tirzepatide administered SC via SDP followed by MUPFP.

The study duration for individual participants, inclusive of screening, is expected to be approximately 14 weeks.

Following is the study design:

2. Statistical Hypotheses

The primary objective of this study is to evaluate bioequivalence of the MUPFP (test) and the SDP (reference) with a 5-mg dose, as assessed using tirzepatide PK parameters C_{max} , $AUC(0-t_{last})$, and $AUC(0-\infty)$ in healthy participants.

3. Analysis Sets

The following analysis sets are defined:

Table 2 Analysis sets

Participant Analysis Set / Population	Description
Enrolled	All randomly assigned participants.
Safety analysis set	All participants who are exposed to study intervention. Participants will be analyzed according to the intervention they actually received.
PK analysis set	All randomly assigned participants who received at least 1 study intervention and have evaluable PK data.
PK completer data set	For each PK primary parameter, only include participants who received all study interventions, and have evaluable PK data for both treatment periods.

4. Statistical Analyses

4.1. General Considerations

Statistical analysis of this study will be the responsibility of Eli Lilly and Company or its designee.

PK analyses will be conducted for the PK analysis set according to the actual tirzepatide formulation received. Safety analyses will be conducted with the safety analysis set.

Summary statistics and statistical analysis will only be presented for data where detailed in this SAP. For continuous data, summary statistics will include the arithmetic mean, arithmetic standard deviation (SD), median, min, max and N; for log-normal data (eg, the PK parameters: area under the concentration versus time curve [AUCs] and maximum observed drug concentration [C_{max}]) the geometric mean and geometric coefficient of variation (CV%) will also be presented. For categorical data, frequency count and percentages will be presented. Data listings will be provided for all subjects up to the point of withdrawal. Summary statistics and statistical analyses will generally only be performed for subjects included in the relevant analysis population. For the calculation of summary statistics and statistical analysis, unrounded data will be used.

Mean change from baseline is the mean of all individual subjects' change from baseline values. Each individual change from baseline will be calculated by subtracting the individual subject's baseline value from the value at the timepoint. The individual subject's change from baseline values will be used to calculate the mean change from baseline using a SAS procedure such as Proc Univariate.

Data analysis will be performed using SAS[®] Version 9.4 or greater.

Additional exploratory analyses of the data will be conducted as deemed appropriate. Study results may be pooled with the results of other studies for safety and population PK analysis purposes

4.2. Participant Dispositions

Subject disposition will be listed. Subject ID, date of study discontinuation, reason for discontinuation, adverse events for discontinuation due to AE, and last dose information (treatment, study period, study day) will be listed.

The demographic variables age, sex, race, ethnicity, body weight, height and body mass index will be summarized and listed. All other demographic variables will be listed only.

4.3. Primary Analysis

4.3.1. Pharmacokinetic analysis

Pharmacokinetic parameter estimates will be determined using non-compartmental procedures in validated software program (Phoenix WinNonlin Version 8.1 or later).

Plasma concentrations of tirzepatide (LY3298176) will be used to determine the following PK parameters, when possible:

Parameter	Units	Definition
AUC(0-t _{last})	ng.h/mL	area under the concentration versus time curve from time zero to time t, where t is the last timepoint with a measurable concentration
AUC(0-∞)	ng.h/mL	area under the concentration versus time curve from time zero to infinity
%AUC(t _{last} -∞)	%	percentage of AUC (0-∞) extrapolated
C _{max}	ng/mL	maximum observed drug concentration
t _{max}	h	time of maximum observed drug concentration
t _{1/2}	h	half-life associated with the terminal rate constant (λ_z) in non-compartmental analysis
CL/F	L/h	apparent total body clearance of drug calculated after extra-vascular administration
V _z /F	L	apparent volume of distribution during the terminal phase after extra-vascular administration

Additional PK parameters may be calculated, as appropriate.

The software and version used for the final analyses will be specified in the clinical study report. Any exceptions or special handling of data will be clearly documented within the final study report.

Formatting of tables, figures and abbreviations will follow the Eli Lilly Global PK/PD/TS Tool: NON-COMPARTMENTAL PHARMACOKINETIC STYLE GUIDE. The version of the tool effective at the time of PK analysis will be followed.

General PK Parameter Rules

- Actual sampling times will be used in the final analyses of individual PK parameters, except for non-bolus pre-dose sampling times which will be set to zero.
- C_{max} and t_{max} will be reported from observed values. If C_{max} occurs at more than one timepoint, t_{max} will be assigned to the first occurrence of C_{max}.
- AUC parameters will be calculated using a combination of the linear and logarithmic trapezoidal methods (linear-log trapezoidal rule). The linear trapezoidal method will be applied up to t_{max} and then the logarithmic trapezoidal method will be used after t_{max}. The minimum requirement for the calculation of AUC will be the inclusion of at least three consecutive concentrations above the lower limit of quantification (LLOQ), with at least one of these concentrations following C_{max}.

- AUC(0-∞) values where the percentage of the total area extrapolated is more than 20% will be flagged. Any AUC(0-∞) value excluded from summary statistics will be noted in the footnote of the summary table.
- Half-life ($t_{1/2}$) will be calculated, when appropriate, based on the apparent terminal log-linear portion of the concentration-time curve. The start of the terminal elimination phase for each subject will be defined by visual inspection and generally will be the first point at which there is no systematic deviation from the log-linear decline in serum concentrations. Half-life will only be calculated when a reliable estimate for this parameter can be obtained comprising of at least 3 data points. If $t_{1/2}$ is estimated over a time window of less than 2 half-lives, the values will be flagged in the data listings. Any $t_{1/2}$ value excluded from summary statistics will be documented in the footnote of the summary table.
- A uniform weighting scheme will be used in the regression analysis of the terminal log-linear portion of the concentration-time curve.
- The parameters based on the last observed quantifiable drug concentration (C_{last}) will be reported.

Individual PK Parameter Rules

- Only quantifiable concentrations will be used to calculate PK parameters with the exception of special handling of certain concentrations reported below the lower limit of quantification (BQL). Plasma concentrations reported as BQL will be set to a value of zero when all of the following conditions are met:
 - The compound is non-endogenous.
 - The samples are from the initial dose period for a subject or from a subsequent dose period following a suitable wash-out period.
 - The timepoints occur before the first quantifiable concentration.
- All other BQL concentrations that do not meet the above criteria will be set to missing.
- Also, where two or more consecutive concentrations are BQL towards the end of a profile, the profile will be deemed to have terminated and therefore any further quantifiable concentrations will be set to missing for the calculation of the PK parameters unless it is considered to be a true characteristic of the profile of the drug.

Individual Concentration vs. Time Profiles

- Individual concentrations will be plotted utilizing actual sampling times.
- The terminal point selections will be indicated on a semi-logarithmic plot.

Average Concentration vs. Time Profiles

- The average concentration profiles will be graphed using scheduled (nominal) sampling times.
- The average concentration profiles will be graphed using arithmetic average concentrations.
- The pre-dose average concentration for single-dose data from non-endogenous compounds will be set to zero. Otherwise, only quantifiable concentrations will be used to calculate average concentrations.
- Concentrations at a sampling time exceeding the sampling time window specified in the protocol, or $\pm 10\%$, will be excluded from the average concentration profiles.
- Concentrations excluded from the mean calculation will be documented in the final study report.
- A concentration average will be plotted for a given sampling time only if 2/3 of the individual data at the timepoint have quantifiable measurements that are within the sampling time window specified in the protocol or $\pm 10\%$. An average concentration estimated with less than 2/3 but more than 3 data points may be displayed on the mean concentration plot if determined to be appropriate and will be documented within the final study report.

Treatment of Outliers during Pharmacokinetic Analysis

Application of this procedure to all PK analyses is not a requirement. Rather, this procedure provides justification for exclusion of data when scientifically appropriate. This procedure describes the methodology for identifying an individual value as an outlier for potential exclusion but does not require that the value be excluded from analysis. The following methodology will not be used to exclude complete profiles from analysis.

Data within an Individual Profile

A value within an individual profile may be excluded from analysis if any of the following criteria are met:

- For PK profiles during single dosing of non-endogenous compounds, the concentration in a pre-dose sample is quantifiable.
- For any questionable datum that does not satisfy the above criteria, the profile will be evaluated, and results reported with and without the suspected datum.

Data between Individual Profiles

1. If $n < 6$, then the dataset is too small to conduct a reliable range test. Data will be analyzed with and without the atypical value, and both sets of results will be reported.

2. If $n \geq 6$, then an objective outlier test will be used to compare the atypical value to other values included in that calculation:
 - a. Transform all values in the calculation to the logarithmic domain.
 - b. Find the most extreme value from the arithmetic mean of the log transformed values and exclude that value from the dataset.
 - c. Calculate the lower and upper bounds of the range defined by the arithmetic mean $\pm 3*SD$ of the remaining log-transformed values.
 - d. If the extreme value is within the range of arithmetic mean $\pm 3*SD$, then it is not an outlier and will be retained in the dataset.
 - e. If the extreme value is outside the range of arithmetic mean $\pm 3*SD$, then it is an outlier and will be excluded from analysis.

If the remaining dataset contains another atypical datum suspected to be an outlier and $n \geq 6$ following the exclusion, then repeat step 2 above. This evaluation may be repeated as many times as necessary, excluding only one suspected outlier in each iteration, until all data remaining in the dataset fall within the range of arithmetic mean $\pm 3*SD$ of the log-transformed values.

Reporting of Excluded Values

Individual values excluded as outliers will be documented in the final report. Approval of the final report will connote approval of the exclusion.

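### SAP 4.3.1 has a ±3 SD outlier rule that is not kept out of the bioequivalence models, and at this sample size it promises no result with the flagged value retained

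*SAP*

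**What the plan says.** The outlier procedure is in SAP 4.3.1, within 4.3 Primary Analysis. Its preamble is permissive. It states "Application of this procedure to all PK analyses is not a requirement", offers grounds for leaving data out where that is scientifically justified, and adds that identifying an outlier "does not require that the value be excluded from analysis". It sets one limit: "The following methodology will not be used to exclude complete profiles from analysis".

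The branches then differ:

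- **Within a profile.** A quantifiable predose concentration may be excluded. For any other questionable value, "the profile will be evaluated, and results reported with and without the suspected datum".
- **Between profiles, n < 6.** "Data will be analyzed with and without the atypical value, and both sets of results will be reported".
- **Between profiles, n ≥ 6.** A test is used to "compare the atypical value to other values included in that calculation". The most extreme log value is set aside and compared with the mean ± 3 SD of the rest. If it lies outside, "then it is an outlier and will be excluded from analysis". The rule can run again: "This evaluation may be repeated as many times as necessary, excluding only one suspected outlier in each iteration".

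Excluded values are to be documented in the final report, and approval of that report counts as approval of the exclusion. SAP 4.3.2, which defines the mixed-effects and fixed-effects bioequivalence models, does not mention outliers. The PK analysis set and the PK completer data set (SAP 3) depend on evaluable PK data, a term not linked to the outlier rule.

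**The concern.** With about 54 completers, any between-participant test on a primary parameter falls in the n ≥ 6 branch. That branch gives no criterion beyond the statistical one and does not commit to showing the confidence interval with the value retained.

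The trial compares injection devices. A very low exposure may be an incomplete injection, which is part of what is being compared and not noise around it. The study is open-label, so the choice to invoke an optional test could be made with device and result known. If the rule reaches Cmax or AUC, the bioequivalence verdict could depend on a choice that the plan has not fixed in advance.

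**Working it through.** **1. Reproduce the plan's figure.** Inputs from SAP 5 and 4.3.2: N = 54, within-subject CV 24%, ratio 1.05, limits 0.80 to 1.25, 90% CI.

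- Log-scale SD = √ln(1 + 0.24²) = 0.2366.
- SE = 0.2366 × √(2/54) = 0.0455, with 52 df.
- Exact power of the two one-sided tests = 98.35%, consistent with the stated 95% or more.

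**2. One failed dose, by hand.** Assume 27 participants per sequence and one dose delivering a fraction f.

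- The mean log ratio shifts by ln(f)/54, down for an MUPFP dose and up for an SDP dose.
- The variance of the within-participant log difference rises from 2 × 0.2366² = 0.1120 by ln(f)² × (1 − 1/27)/52.
- For f = 0.10 the rise is 5.302 × 0.963/52 = 0.0982, giving 0.2102.
- CI half-width = 1.675 × √(0.2102 × (2/27)/4) = 0.1045. The full width is 0.209, against 0.153 without the failed dose.

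With the value kept, a pass needs the estimate to lie within ±(0.2231 − 0.1045) = ±0.1186:

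- *MUPFP dose, ratio 0.95 otherwise.* Overall ratio 0.95 × 0.10^(1/54) = 0.910, log −0.0939. Φ((0.1186 − 0.0939)/0.0455) ≈ 71%.
- *SDP dose, ratio 1.05.* Overall ratio 1.05/0.10^(1/54) = 1.096, log 0.0914. Φ((0.1186 − 0.0914)/0.0455) ≈ 73%.
- *MUPFP dose, ratio 1.05.* Overall ratio 1.006, log 0.0061. About 99%.

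With the value dropped, 53 pairs remain and the half-width is 0.077. The pass rate is about 98% at either ratio.

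**3. Simulation of the rule.** Steps 2a to 2e were iterated by device on one parameter and every flagged value was dropped with its pair, at between-subject CV 15%, 30% and 45%, with 10,000 runs per scenario.

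| Scenario | Kept | Dropped |
|---|---|---|
| Clean, ratio 1.05 | 98% | 98% |
| Clean, true ratio 0.80 (false positive rate) | 4.8–5.0% | 4.9–5.3% |
| One MUPFP dose at 50%, ratio 0.95 | 96% | 96–97% |
| One MUPFP dose at 25%, ratio 0.95 | 90% | 94–98% |
| One MUPFP dose at 10%, ratio 0.95 | 70–71% | 96–98% |
| One MUPFP dose at 10%, ratio 1.05 | 99% | 98% |
| One SDP dose at 10%, ratio 1.05 | 72–73% | 97–98% |

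A mixed model that keeps the unpaired value agreed with pairwise deletion to within 0.4 points for one MUPFP dose at 10% with ratio 0.95. In separate clean-data runs at similar between-subject variability, the rule flagged at least one value in roughly 40% of datasets. If the test is run routinely, the keep-or-drop question would therefore arise often without any misdelivery.

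**4. The complete-profile sentence.** A failed injection lowers Cmax and both AUCs together. Requiring all three to pass (assumed Cmax–AUC correlation 0.5 to 0.9), one MUPFP dose at 10% with ratio 0.95 gives:

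- all data: 54–63%
- all three values may be dropped: 93–97%
- a dose flagged on all three counts as a complete profile and is kept: 53–63%

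How that undefined term is read decides whether the rule has a large effect or almost none in this case.

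**The case against.** The strongest reply is that the procedure is hedged. It is optional, it speaks of exclusion where scientifically justified, it starts from a value already thought atypical, and it will not remove complete profiles. Step 2e can be read as the last step of an algorithm that binds only once invoked. Exclusions are documented and data are listed, so a reader could recompute the all-data interval.

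Much of this stands. A reader might infer that the SAP requires Cmax and AUC outliers to be deleted from the primary models. It does not say so; this is a use the text leaves open. A reader might also see a flat contradiction between preamble and step 2e. The reading in which the test is optional to invoke and binding once invoked is plausible, though not written. Nor does the SAP promise paired results everywhere else: a quantifiable predose value may be dropped without them. The footnote rules for AUC(0-∞) and half-life values excluded from summary statistics only require a note and do not confine the outlier rule.

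The large contrasts also need near-total loss of a dose, an otherwise unfavourable ratio or a failure of the reference pen, and the less protective reading of a complete profile.

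What remains is that none of the hedges names the analyses covered, defines a complete profile, or commits to a result with the value kept. Documenting an excluded value is not the same as reporting the interval that includes it.

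**Conclusion.** The point holds as a gap in prespecification that should be fixed. No stated figure is wrong: the sample size and power reproduce. On clean data the effect on power and on the false positive rate is negligible.

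The exposure is to rare extreme values. One MUPFP dose at 10% with ratio 0.95 moves the pass rate from about 70% to about 97%, and one SDP dose at 10% with ratio 1.05 from about 72% to about 97%. At the planned ratio, one such MUPFP dose makes no practical difference, and at 50% delivery with ratio 0.95 neither does the rule. These figures assume one parameter, N = 54, within-subject CV 24%, between-subject CV 15–45%, and the rule run by device with every flagged value dropped. The documents give no misdelivery rate and no between-subject CV.

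A reader might infer that the rule produces false passes. These single-dose examples do not show that: the overall ratio with the failed MUPFP dose is still 0.91, inside the limits. What changes is the verdict, not its correctness at the boundary.

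**What to change.** In SAP 4.3.1 and 4.3.2:

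1. State that the bioequivalence models use all evaluable Cmax, AUC(0-tlast) and AUC(0-∞) values, and that a value flagged only by the ±3 SD test stays in the PK analysis set and the PK completer data set.
2. Report any trimmed result only as a sensitivity analysis beside the all-data result. This extends what the SAP already promises for n < 6.
3. Align step 2e with the preamble, and say whether removing a participant's Cmax and both AUCs for a dose counts as excluding a complete profile.

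The cost is a paragraph of text and one extra model run per parameter if a value is flagged. The real downside is a wider 90% CI when a genuine extreme value occurs: with one 10% dose the simulated mean log-scale width is 0.208 with the value kept, against 0.152–0.155 with it dropped. The chance of declaring bioequivalence can then be lower. Stating only the scope and committing to both results would close the reporting gap, but would leave open which result decides.
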